3.14 Dispense Study Drug

Study drug will be dispensed to subjects beginning at Baseline (Day 1) and as specified in Section 2. The first dose of study drug will be administered after all other Baseline (Day 1) procedures are completed. At the visits specified in Section 2.1, the site personnel will review returned study drug kits, and empty study drug packaging to verify compliance.

Study drug (i.e., ABBV-3067, ABBV-2222, and respective placebos) should be dosed together and taken within approximately 1 hour after a meal. Study drugs will need to be taken at the investigative site at the Day 1 and Day 15 visits. The site will provide meals at those visits. Subjects should be instructed to take their study medications at the same time every day.

3.15 Clinical Laboratory Tests

The blood samples for serum chemistry tests will be collected prior to study drug dosing on Day 1 and Day 15. Fasting or non-fasting status will be recorded in the source documents and on the laboratory requisition. The baseline laboratory test results for clinical assessment for a particular test will be defined as the last measurement prior to the initial dose of study drug.

Samples will be obtained for the laboratory tests listed in Table 1 at the time points specified in Section 2.

Table 1. Clinical Laboratory Tests

Hematology ^a	Clinical Chemistry ^a	Other Tests
Hematocrit Hemoglobin Mean Corpuscular volume White blood cell count Neutrophils Lymphocytes Monocytes Eosinophils Reticulocyte count Platelet count (estimate not acceptable) Bands (if present)	hsCRP Blood urea nitrogen Creatinine Total bilirubin Direct and indirect bilirubin Alanine aminotransferase (ALT) Aspartate aminotransferase (AST) Alkaline phosphatase Sodium Potassium Calcium Inorganic phosphorus Total protein Glucose Albumin Chloride Bicarbonate	Urine: ^b drugs of abuse and alcohol Urine ^f and serum human chorionic gonadotropin ^{b,c,d} follicle-stimulating hormone ^{b,c,e} Urinalysis: ^a Specific gravity Ketones pH Protein Glucose Blood Bilirubin Leukoesterase Nitrites Microscopic examination, if indicated
Coagulation^a		Serology^b
Prothrombin time (PT)/INR Activated partial thromboplastin time (aPTT)	Creatinine clearance (Cockcroft-Gault calculation) Gamma-glutamyl transferase (GGT) Uric acid Lactate dehydrogenase Creatine phosphokinase Cholesterol Triglycerides	HBsAg Anti-HCV antibody HIV-1 and HIV-2 antibodies

INR = international normalized ratio, HBsAG = Hepatitis B virus surface antigen, HCV = Hepatitis C virus, HIV = Human immunodeficiency virus, hsCRP = High-sensitivity C-reactive protein

- a. Chemistries, hematology, coagulation and urinalysis labs should be performed at all visits.
- b. Performed only at screening.
- c. Females only.
- d. Pregnancy testing is not required for females of non-childbearing potential.
- e. If needed to determine postmenopausal status.
- f. Local test.

A certified laboratory will be utilized to process and provide results for the clinical laboratory tests. Laboratory reference ranges will be obtained prior to the initiation of the study.

Instructions regarding the collection, processing, and shipping of these samples will be provided by the central laboratory and sent to the following certified laboratory addresses:

Covance CLS
[name]
[name]
USA

Covance Central Laboratory Services S.A.
[name]
[name]
Switzerland

ERT
[name]
[name]
USA

ERT
[name]
[name]
Germany

If a laboratory test value is outside the reference range and the investigator considers the laboratory result to be clinically significant, the investigator will:

- repeat the test to verify the out-of-range value using the appropriate Central lab kit;
- follow the out-of-range value to a satisfactory clinical resolution;
- if deemed appropriate, discontinue the subject from the study or require the subject to receive treatment; in this case, the laboratory result will be recorded as an AE;
- document the result and appropriate follow-up in the subject's source records and applicable eCRFs.

Pregnancy Tests (Serum and Urine)

Pregnancy testing should be performed only for women of childbearing potential.

A qualitative serum pregnancy test will be performed at Screening for all female subjects of childbearing potential. The serum pregnancy test will be sent to and performed by the central laboratory. If the serum pregnancy test is positive, the subject is considered a screen failure. If the serum pregnancy test is borderline, it should be repeated ≥ 3 days later to determine eligibility.

If the repeat serum pregnancy test is:

- Positive, the subject is considered a screen failure;
- Negative, the subject can be enrolled into the trial;

- Still borderline, ≥ 3 days later, this will be considered documentation of continued lack of a positive result and the subject can be enrolled into the study (unless prohibited per local requirements) in the absence of clinical suspicion of pregnancy and other pathological causes of borderline results.

Additional urine pregnancy tests will be performed at visits indicated in the Activity Schedule (Protocol Appendix D) and Section 2. More frequent pregnancy tests can be performed throughout the study at the investigator's discretion or if required per local/country requirements.

- If the baseline urine pregnancy test is negative, then dosing with study drug may begin.
- If the baseline or post-baseline urine pregnancy test is positive, dosing with study drug must be withheld and a serum pregnancy test is required (as stated above). If the serum pregnancy test is positive, the subject should be discontinued from the study.
- Unless a woman is suspected to have become pregnant, additional pregnancy testing during the clinical trial is not necessary.

A serum pregnancy test will also be performed at the post-treatment Day 30 follow-up visit if the urine pregnancy test at this visit is positive.

Urinalysis

Dipstick urinalysis will be completed by the central laboratory at all required visits. Specified abnormal macroscopic urinalyses defined as leukocytes, nitrite, protein, ketones, or blood greater than negative, or glucose greater than normal will be followed up with a microscopic analysis at the central laboratory.

3.16 Subject Withdrawal from Study

If subjects prematurely discontinue from the study, they should be asked to return for a Premature Discontinuation visit and participate in a 30-day follow-up visit if possible.

[figure not shown]
All attempts must be made to determine the date of the last study drug dose and the primary reason for discontinuation of study drug or study participation. The information will be recorded on the appropriate eCRF page. However, these procedures should not interfere with the initiation of any new treatments or therapeutic modalities that the investigator feels are necessary to treat the subject's condition. Following discontinuation of study drug, the subject will be treated in accordance with the investigator's best clinical judgment, irrespective of whether or not the subject decides to continue participation in the study.

4 SAFETY MANUAL

4.1 Methods and Timing of Safety Assessment

All serious adverse events (SAEs) as well as protocol-related nonserious AEs (e.g., bruising at phlebotomy site, done during Screening) will be collected from the time the subject signed the study-specific informed consent until study drug administration. From the time of study drug

administration until 30 days after discontinuation of study treatment, all AEs and SAEs will be collected whether solicited or spontaneously reported by the subject.

4.2 Recording Data and Analyses of Safety Findings

AEs will be coded using the Medical Dictionary for Regulatory Activities (MedDRA). The number and percentage of subjects with treatment-emergent adverse events (i.e., any event that begins or worsens in severity after initiation of study drug through 30 days post-study drug dosing) will be tabulated by primary MedDRA System Organ Class (SOC) and preferred term (PT). The tabulation of the number of subjects with treatment-emergent AEs by severity grade and relationship to study drug also will be provided. Subjects reporting more than 1 AE for a given MedDRA preferred term will be counted only once for that term using the most severe grade according to the severity grade table and the most related according to the relationship to study drug tables. Subjects reporting more than 1 type of AE within an SOC will be counted only once for that SOC.

Adverse Events of Special Interest

Isolated instances of nonserious, generalized, maculopapular rash have occurred in prior Phase 1 studies when ABBV-3067 and ABBV-2222 were administered together (see protocol Section 6.1). All rash AEs are considered adverse events of special interest (AESIs). These AEs have to be reported in real time (i.e., within 24 hours from the time of the knowledge of the event) using a study-specific rash questionnaire ([Appendix B](#)).

Maculopapular and other rash events are to be graded as follows (adapted from Common Terminology Criteria for Adverse Events [CTCAE] version 5.0):

- Grade 1** Macules/papules covering < 10% body surface area (BSA) with or without symptoms (e.g., pruritis, burning, tightness).
- Grade 2** Macules/papules covering 10% to 30% BSA with or without symptoms (e.g., pruritis, burning, tightness); or rash covering > 30% BSA with or without mild symptoms.
- Grade 3** Macules/papules covering > 30% BSA with moderate or severe symptoms.

Note: To calculate the percent of BSA, estimate the area covered by the actual macules/papules and do not include the clear skin between them. Imagine the rash coverage as if all of the macules and papules

coalesce into a single area. A diagram showing the contribution of different body parts to BSA, helpful to calculate % BSA, can be found at:

<https://books.google.com/books?id=3vg8AgAAQBAJ&pg=PP118&lpg=PP118&dq=body+surface+area+calculation+rash+CTCAE+v+4&source=bl&ots=KDrEpHcWGM&sig=ACfU3U3b7vEteEqR7Z1nKhfAmgTwN2L8mw&hl=en&sa=X&ved=2ahUKEwic6KqItJPgAhVQdt8KHVJTBQYQ6AEwDHoECAAQAQ#v=onepage&q=body%20surface%20area%20calculation%20rash%20CTCAE%20v%204&f=false>.

For rash Grade 3, treatment with study drug will be discontinued by the investigator (see Section 6.1 of the protocol).

The medical management of rash will be done at the discretion of the investigator. If the diagnosis is uncertain or if there is concern about a possible severe hypersensitivity reaction, the investigator may elect, at his or her discretion, to perform additional investigations to help define the rash, including but not restricted to a dermatologist or allergist consultation, a skin biopsy, or additional safety laboratories. Results of investigations (consultation reports, skin biopsies, laboratory test results, etc.) should be included with the source documents.

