In prior Phase 1 studies, there were isolated instances of nonserious generalized, maculopapular rash that occurred when ABBV-3067 and ABBV-2222 were administered together. The rashes resolved after study drug discontinuation. Maculopapular rash is a disorder characterized by the presence of macules (flat) and papules (elevated). Also known as morbilliform rash, maculopapular rash is one of the most common cutaneous AEs, frequently affecting the upper trunk, spreading centripetally, and associated with pruritus.

Rash is to be graded according to the CTCAE (adapted) version 5.0.³ All rash cases have to be reported within 24 hours from the time of knowledge of the event. Refer to the Operations Manual ([Appendix F](#)) for details about management of these events.

Adverse Event Severity and Relationship to Study Drug

The investigators will rate the severity of each AE according to the CTCAE version 5.0.³

Grading System for Adverse Events (a semicolon indicated "or" within the description of the grade)

Grade 1	Mild; asymptomatic or mild symptoms; clinical or diagnostic observations only; intervention not indicated
Grade 2	Moderate; minimal, local, or noninvasive intervention indicated; limiting age-appropriate instrumental ADL ^a
Grade 3	Severe or medically significant but not immediately life-threatening; hospitalization or prolongation of hospitalization indicated; disabling; limiting self-care ADL ^b
Grade 4	Life-threatening consequences; urgent intervention indicated
Grade 5	Death related to AE

ADL = Activities of Daily Living

- a. Instrumental ADL refer to preparing meals, shopping for groceries or clothes, using the telephone, managing money, etc.
- b. Self-care ADL refer to bathing, dressing and undressing, feeding self, using the toilet, taking medications, and not bedridden.

The investigator will use the following definitions to assess the relationship of the AE to the use of study drug:

Reasonable Possibility	After consideration of factors including timing of the event, biologic plausibility, clinical judgment, and potential alternative causes, there is sufficient evidence (information) to suggest a causal relationship.
No Reasonable Possibility	After consideration of factors including timing of the event, biologic plausibility, clinical judgment, and potential alternative causes, there is insufficient evidence (information) to suggest a causal relationship.

Pregnancy

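### The Operations Manual grades every rash by macule/papule area and symptoms, so a serious blistering, exfoliative or mucosal rash on 30% BSA or less stays below its mandatory Grade 3 stop

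*Protocol*

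**What the plan says.** **Operations Manual 4.2 (Appendix F to the protocol).** A single adapted scale covers all rash: "Maculopapular and other rash events are to be graded as follows".

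- Grade 1: "Macules/papules covering < 10% body surface area (BSA) with or without symptoms".
- Grade 2: macules/papules on 10% to 30% BSA whatever the symptoms, or "rash covering > 30% BSA with or without mild symptoms".
- Grade 3, the highest grade listed: "Macules/papules covering > 30% BSA with moderate or severe symptoms".

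For the area, the investigator is told to "estimate the area covered by the actual macules/papules and do not include the clear skin between them". The stop rule reads "For rash Grade 3, treatment with study drug will be discontinued by the investigator (see Section 6.1 of the protocol". Beyond that, "The medical management of rash will be done at the discretion of the investigator".

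**Protocol 6.1.** "Rash is to be graded according to the CTCAE (adapted) version 5.0". The same section has every adverse event rated on CTCAE version 5.0 and prints a general Grade 1 to 5 table. On that table, an event for which hospitalization is indicated is Grade 3, and one with life-threatening consequences is Grade 4.

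**Protocol 5.5.** The list of withdrawal reasons opens with a stem saying that a subject *may* be withdrawn. It includes a life-threatening event, a serious event posing immediate risk, and maculopapular rash or another allergic drug reaction of CTCAE version 5.0 Grade 3 or higher. The word adapted does not appear there. The hepatic item in the same list says that drug *must* be stopped.

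**The concern.** The manual sets a compulsory stop for severe rash but defines severity by a feature that some severe rashes lack. Blistering, exfoliation, and mucosal or ocular involvement appear in no grade, although the rash questionnaire (Operations Manual Appendix B) asks about each of them. Grades 1 and 2 apply whatever the symptoms, so no symptom can lift a rash of limited area to Grade 3.

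Two things are at stake. For these rashes, stopping drug rests on judgement and not on a rule. The recorded severity may also be too low: if the adapted grade is the one entered on the adverse event form, the row for events of Grade 3 or higher (SAP 9.2.2) and the maximum-severity table (SAP 9.2.3) would understate such a rash.

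**Working it through.** The plan gives no figure to reproduce here. The check applies each rule to the same cases.

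**Step 1. The adapted scale (Operations Manual 4.2), by macule/papule area.**

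| Macule/papule area | Symptoms | Adapted grade | Manual's compulsory stop |
|---|---|---|---|
| < 10% BSA | any | 1 | no |
| 10% to 30% BSA | any | 2 | no |
| > 30% BSA | none or mild | 2 | no |
| > 30% BSA | moderate or severe | 3 | yes |

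At 30% BSA or less, with 30% included, the maximum is Grade 2. Counting blisters or mucosal lesions as severe symptoms does not change this.

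**Step 2. A rash with no macules or papules.** Only the second part of Grade 2 speaks of rash without requiring macules/papules, and it needs more than 30% BSA with no more than mild symptoms. A rash of this kind on a larger area with moderate or severe symptoms fits no grade as written.

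**Step 3. The adapted scale against the general table.** Take a blistering rash for which hospitalization is indicated, which is Grade 3 in protocol 6.1.

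- Macules/papules on 8% BSA: adapted Grade 1, so the difference is 3 − 1 = 2 grades.
- Macules/papules on 20% BSA: adapted Grade 2, so the difference is 3 − 2 = 1 grade.

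The manual's stop does not trigger in either case.

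**Step 4. The routes left in protocol 5.5.** If the rash is an allergic drug reaction and is graded on CTCAE version 5.0 without the adaptation, it meets the withdrawal criterion. If the site carries the adapted grade over, as protocol 6.1 could be read to require, it does not. The routes for a life-threatening event and for a serious event with immediate risk do not depend on grade. All of these sit under the *may* stem. A *must* is written for the hepatic criteria in 5.5 and for pregnancy in 6.1, but protocol 5.5 contains none for rash.

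**Step 5. The cross-references.** Protocol 6.2 sends the reader to the manual for rash management. The manual's stop rule cites protocol 6.1, which holds the special-interest and grading text. The withdrawal criterion is in 5.5, so a site following the citations does not reach it.

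**The case against.** The strongest reply is that protocol 5.5 already covers these patients. Its rash item reaches allergic drug reactions in general, is not tied to BSA and does not mention the adapted scale, so the hospitalization example can qualify at 8% or 20% BSA. The *may* stem is weak evidence that an item is optional: pregnancy is a bare item under the same stem, yet 6.1 makes discontinuation compulsory. The rashes described from earlier studies were nonserious and mild to moderate, and those seen when the two drugs were given together in Phase 1 were maculopapular. A scale built around that signal is defensible, given investigator discretion, optional specialist referral and reporting within 24 hours.

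Much of this stands, and it is why the point is minor. A reader might infer that the plan leaves no way to stop drug for a blistering or mucosal rash; 5.5 shows otherwise. What survives is that pregnancy and the hepatic criteria each have a *must* and these rashes have none, and that no document says which grade prevails when the two scales differ.

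A reader might also infer that such a rash would be missing from the safety tables. It would not. Once the subject is admitted, the event is serious by the definition in 6.1. It then appears among the serious events in SAP 9.2.2 and, if the product-specific rash query identifies it, in the serious rash rows of SAP 9.2.5, whatever its grade. Only the grade-based outputs are exposed.

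It is also tempting to ask for a compulsory stop for any blistering, exfoliative or mucosal rash regardless of area. That is a clinical preference which nothing in the documents supports.

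**Conclusion.** The point holds as a minor one. On the manual's own wording, a rash with macules/papules on 30% BSA or less cannot reach Grade 3, whatever its morphology, so the manual's compulsory stop cannot apply to it. In the worked cases the adapted grade is one or two grades below the general one. This is a stated rule that gives the wrong grade for some rashes, and not merely a missing detail.

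The practical gap is small, because protocol 5.5, investigator discretion, rapid rash reporting and review by the data monitoring committee all remain. The documents give no rate for such rashes, so no number of affected subjects is offered. The effect on the severity tables assumes that the adapted grade is the one entered on the adverse event form, which no document settles. Efficacy analyses and sample size are not affected.

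**What to change.** 1. In Operations Manual 4.2, restrict the area scale to maculopapular rash without blistering, exfoliation, or mucosal or ocular involvement.
2. Grade every other rash on the Grade 1 to 5 table in protocol 6.1, together with any rash that is life-threatening or for which hospitalization is indicated. Where both scales apply, take the higher grade, and state that this is the grade entered on the adverse event form.
3. In Operations Manual 4.2 and protocol 5.5, make the drug stop mandatory for rash of Grade 3 or higher graded in this way.
4. Have the manual cite protocol 5.5 for the stop.

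The cost is wording in the two documents and a note to sites; as a protocol amendment it needs the ethics review described in protocol 8.1. No new procedure or data item is needed, because the questionnaire already records the relevant features and the general table already exists. The downside is that a few subjects may stop drug earlier than they would under the present text.

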4.3 Reporting Adverse Events and Intercurrent Illnesses

In the event of an SAE, whether associated with study drug or not, the investigator will notify Clinical Pharmacovigilance within 24 hours of the site being made aware of the SAE by entering the SAE data into the electronic data capture (EDC) system. SAEs that occur prior to the site having access to the RAVE® system, or if RAVE is not operable, should be documented on the SAE nonCRF forms and emailed (preferred route) or faxed to Clinical Pharmacovigilance within 24 hours of the site being made aware of the SAE.

Email: [contact]

FAX to: [contact]

For safety concerns, contact AbbVie's General Medicine Safety Team at:

General Medicine Safety Team

[REDACTED]

[name]
[name]

[contact]

Email: [contact]

For any subject safety concerns, please contact the physician listed below:

Primary Therapeutic Area Medical Director

MEDICAL CONTACT:

[REDACTED]

AbbVie Inc.

[REDACTED]

[name]

[name]

Contact Information:

Office:

[REDACTED]

Mobile:

[REDACTED]

Fax:

[REDACTED]

Email:

[REDACTED]

In emergency situations involving study subjects when the primary Therapeutic Area Medical Director is not available by phone, please contact the 24-hour AbbVie Medical Escalation Hotline where your call will be re-directed to a designated backup AbbVie Therapeutic Area Medical Director:

[contact]

The sponsor will be responsible for Suspected Unexpected Serious Adverse Reactions (SUSAR) reporting for the Investigational Medicinal Product (IMP) in accordance with Directive 2001/20/EC.

5 COUNTRY-SPECIFIC REQUIREMENTS

5.1 SUSAR Reporting

AbbVie will be responsible for suspected unexpected serious adverse reactions (SUSAR) reporting for the investigational medicinal product (IMP) in accordance with global and local guidelines and Appendix A of the Investigator Brochure will serve as the Reference Safety Information (RSI). The RSI in effect at the start of a DSUR reporting period serves as the RSI during the reporting period. For follow-up reports, the RSI in place at the time of occurrence of the 'suspected' Serious Adverse Reaction will be used to assess expectedness.

6 STUDY DRUG

6.1 Treatments Administered

In Part 1, the study drugs ABBV-3067 or placebo will be dispensed in the form of film-coated tablets, and the study drugs ABBV-2222 or placebo will be dispensed in the form of capsules at the visits listed in

Section 2.1. In Part 2, the study drugs ABBV-3067 or placebo and ABBV-2222 or placebo will be dispensed in the form of capsules at the visits listed in Section 2.1. Subjects will be instructed to take study drugs once daily at the same time in the morning every day within approximately 1 hour after a meal.

Dosing times for the Day 1 and Day 15 visits and for the 3 doses before the Day 15 and Day 29 visits will be captured in the source records and eCRFs, as specified in Section 3.5.

Study drug must not be dispensed unless the IRT system is contacted. Study drug may only be dispensed to subjects enrolled in the study through the IRT system. At the end of the Treatment Period or at the Premature Discontinuation visit, the site will contact the IRT system to provide visit date information and study drug return information for each kit.

